5.7.2 Laser Photocoagulation

Patients assigned to the laser photocoagulation treatment group will receive laser treatment on day 1.

Repeat laser photocoagulation at months 3, 6, and 9 will be administered if both of the following conditions are met:

- OCT central subfield ≥ 250 µm with Stratus III (Zeiss), ≥ 275 with Cirrus (Zeiss) or ≥ 300 µm with Spectralis (Heidelberg)
- patient might benefit from retreatment in the opinion of the investigator

Laser treatment will be given according to the modified ETDRS treatment protocol (Section 12.1.11).

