6.4.2 Optical Coherence Tomography

OCT is a laser-based, noninvasive, diagnostic system providing high-resolution imaging optical sections of the retina. The mean retinal thickness in the 1-mm central subfield of the SE will be captured using time-domain OCT (Stratus III, Zeiss) or spectral-domain OCT (Cirrus, Zeiss or Spectralis, Heidelberg). Electronic OCT images will be collected for evaluation by a reading center. Once an OCT instrument has been selected for a patient, that instrument must be used for all the study assessments for that patient for the duration of the study.

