7.2.2 Secondary Efficacy Variables

Secondary efficacy variables include: ≥ 15 letters improvement from baseline in BCVA at month 12; change from baseline in the retinal thickness based on OCT at month 12; and change from baseline in total leakage area based on FA at month 12.

Change From Baseline in Retinal Thickness Based on OCT

OCT is a laser-based diagnostic system providing high-resolution optical sections of the retina. OCT will be performed at the investigators' sites. The OCT images will be transferred to the reading center and evaluated by the retina specialists of the reading center

700 µg DEX PS DDS

for the SE. The retinal thickness (microns) in the central 1-mm macular subfield based on OCT will be assessed and analyzed as the secondary efficacy variable.

Change From Baseline in Total Leakage Area Based on FA

FA is a technique to examine the circulation of the retina using the dye tracing method. It involves injection of sodium fluorescein into the systemic circulation, and then an angiogram is obtained by photographing the fluorescence emitted after illumination of the retina. The focal and diffuse leakage area based on FA will be assessed. The total leakage area defined as the sum of focal and diffuse leakage area will be computed and analyzed as the secondary efficacy variable.

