12.1.6 Optical Coherence Tomography

The approved equipment for this protocol include the following: the Stratus III (Carl Zeiss Meditec) with software version 4.0 or greater, or Cirrus (Zeiss) or Spectralis (Heidelberg). For sites using the Stratus OCT, at least 6 consecutive radial scans through the macula, each approximately 6 mm in length, will be taken according to Table 1. For sites using the Zeiss Cirrus spectral domain OCT instrument, a Cirrus Macular Cube 512 x 128 scan (128 horizontal scan lines comprised of 512 A-scans) will be required. For sites using the Heidelberg Spectralis OCT instrument images must be acquired in the Volume Scan mode with ART set to 5 (512 by 97 A scans).

Once the OCT instrument has been selected for a patient, that instrument must be used for all the study visits for that patient for the duration of the study.

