4.2 Baseline Characteristics

The following baseline characteristics will be summarized in total and by treatment group.

- Height (meters) and Weight (kilograms)
- Iris color (Blue, Green, Hazel, Brown, Other)
- Iris color groups, defined as Dark (brown, black, other which contains black in comments), Light (blue, green, hazel, other which doesn't contain black in comments)
- Duration of diabetic macular edema (DME) (months) in the study eye, calculated as (randomization date - DME onset date)/30.4
- BCVA score as a continuous variable and BCVA by randomization strata
- Central retinal thickness (CRT) (microns)
- Total area of macular leakage (mm²)
- lens status assessment: Phakic, Pseudophakic or Ahakic

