5.2 Secondary Efficacy Analyses

Data after the 1st escape therapy will be set to missing. For participants who receive escape therapy or terminate early prior to month 12, month 12 data will be imputed using LOCF (Last Observation Carry Forward). The last observation prior to the 1st escape therapy or at early exit will be used for month 12. In the event of mis-randomization with an incorrect stratum, the actual stratum that the participant belongs will be used for statistical analysis.

5.2.1 BCVA Improvement of ≥ 15 Letters from Baseline at month 12

[figure not shown]
Analysis for proportion of participants with 15 or more letters improvement from baseline in BCVA of study eye at month 12 will be done using a Cochran–Mantel-Haenszel (CMH) test stratified by baseline BCVA categories (≥ 34 to ≤ 49 and ≥ 50 to ≤ 70). The 95% confidence intervals for the between-group difference in the proportion will be calculated using normal approximations.

5.2.2 Change from Baseline in Central Retinal Thickness at Month 12

Analysis for change from baseline in central retinal thickness measured by OCT at month 12 will be performed using an ANCOVA model with treatment and baseline BCVA category as the main effects and baseline retinal thickness as the covariate. The between-group difference and the corresponding 2-sided 95% CI in least-square means will be computed using the ANCOVA model.

5.2.3 Change from Baseline in Total Leakage Area at Month 12

The total area of macular leakage measured by FA is defined as the sum of focal and diffuse leakage area. Analysis for change from baseline in total leakage area at month 12 will be performed using an ANCOVA model with treatment and baseline BCVA categories as the main effects and baseline total leakage area as the covariate. The between-group difference and the corresponding 2-sided 95% CI in least-square means will be computed using the ANCOVA model.

6. Safety Analyses

The safety analysis will be based on safety population using observed data.

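### The central retinal thickness ANCOVA adjusts for raw baseline microns from three OCT devices without a device term: a small, removable loss of precision, with no systematic bias expected

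*SAP*

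**What the plan says.** Protocol 6.4.2 allows mean central subfield thickness to be "captured using time-domain OCT (Stratus III, Zeiss) or spectral-domain OCT (Cirrus, Zeiss or Spectralis, Heidelberg", so one time-domain and two spectral-domain instruments feed the same endpoint. The same section requires consistency within a patient: "Once an OCT instrument has been selected for a patient, that instrument must be used for all the study assessments for that patient". Protocol 12.1.6 repeats this and sets out scan settings by type of site, for example "For sites using the Stratus OCT, at least 6 consecutive radial scans through the macula".

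For repeat laser, Protocol 5.7.2 sets a different threshold for each device: "OCT central subfield ≥ 250 µm with Stratus III (Zeiss), ≥ 275 with Cirrus (Zeiss) or ≥ 300 µm with Spectralis (Heidelberg". The Protocol Summary gives the same three values.

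For the endpoint, Protocol 7.2.2 states: "The retinal thickness (microns) in the central 1-mm macular subfield based on OCT will be assessed and analyzed as the secondary efficacy variable". SAP 5.2.2 specifies an "ANCOVA model with treatment and baseline BCVA category as the main effects and baseline retinal thickness as the covariate", and Protocol 7.3.2 lists the same terms. SAP 4.2 includes "Central retinal thickness (CRT) (microns" among the baseline characteristics, summarised in total and by treatment group. The visible text of either document contains no device term, device stratum, conversion to a common scale or analysis by device.

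**The concern.** Using three cut-offs for one retreatment decision suggests that the plan's authors expect the instruments to give different readings for a similar degree of edema. The analysis model does not carry that expectation over. If the gaps reflect a real offset, a Spectralis eye enters the ANCOVA with a baseline 50 µm higher than an equally swollen Stratus eye, and the model treats the difference as severity.

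The efficiency of the baseline adjustment for one secondary endpoint is at stake, together with the meaning of the baseline thickness summary, whose pooled mean would combine three scales. The primary endpoint, BCVA, is not affected.

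**Working it through.** **Inputs from the documents.** Cut-offs of 250, 275 and 300 µm (Protocol 5.7.2); three permitted devices, one per patient (Protocol 6.4.2, 12.1.6); model terms (SAP 5.2.2, Protocol 7.3.2); about 356 patients at about 20 sites (Protocol 4.1); 1:1 allocation stratified by BCVA category within site (Protocol 5.5).

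**Assumptions, not in the documents.** The device offset d is constant and equals the gap between cut-offs. The slope b of change on true baseline is -0.5 to -0.9; true baseline SD S_b is 100 or 150 µm; residual SD S_r is 80 or 120 µm. The device mix is varied.

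**Step 1: gaps.** 275 - 250 = 25; 300 - 275 = 25; 300 - 250 = 50 µm. The plan states no figure for the precision of the thickness comparison, so these are its only numbers to reproduce.

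**Step 2: outcome.** With one device per patient, (Y12 + d) - (Y0 + d) = Y12 - Y0. A constant offset drops out of the change score.

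**Step 3: covariate.** The baseline entered is Y0 + d. Two eyes with equal edema, one on Spectralis and one on Stratus, get predicted changes that differ by |b| × 50, from 0.5 × 50 = 25 to 0.9 × 50 = 45 µm. This is a shift in an individual prediction, not in the treatment difference.

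**Step 4: offset variance V**, with offsets 0, 25 and 50 µm.
- Equal thirds: (625 + 0 + 625)/3 = 416.7 µm²
- Half Stratus, half Spectralis: 25² = 625 µm²
- Half Cirrus, half Spectralis: 12.5² = 156.3 µm²

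The share of covariate variance due to device is V/(S_b² + V), from 156.3/22,656 = 0.7% to 625/10,625 = 5.9%. The fitted slope is pulled toward zero by the same share. This is the blurring of the baseline adjustment.

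**Step 5: residual variance.** With device omitted it is b²S_b² + S_r² - (bS_b²)²/(S_b² + V), which equals S_r² + b²·S_b²V/(S_b² + V). The relative inflation is b²·S_b²V/[(S_b² + V)·S_r²], and the SE factor is the square root of one plus that.

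| Device mix | Smallest (b -0.5, S_b 100, S_r 120) | Largest (b -0.9, S_b 150, S_r 80) | SE increase |
|---|---|---|---|
| Equal thirds | 0.25 × 400.0/14,400 = 0.7% | 0.81 × 409.1/6,400 = 5.2% | 0.3% to 2.6% |
| Half Stratus, half Spectralis | 0.25 × 588.2/14,400 = 1.0% | 0.81 × 608.1/6,400 = 7.7% | 0.5% to 3.8% |
| Half Cirrus, half Spectralis | 0.25 × 153.8/14,400 = 0.3% | 0.81 × 155.2/6,400 = 2.0% | 0.1% to 1.0% |

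As one device comes to dominate, V and the inflation go to zero.

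**Step 6: simulation of the treatment difference.** Settings: 356 patients, 20 sites, one device per site, offsets 0/25/50 µm, true baseline SD 80, 120 or 150 µm, slope -0.5 or -0.8, residual SD 100 µm, treatment effect -50 µm, equal thirds or half Stratus and half Spectralis, 1,000 runs per scenario. The mean SE was 10.62 to 10.81 µm without a device term and 10.57 to 10.65 µm with it. Within scenarios the reduction was about 0.2% to 1.8%. As a check on scale, 2 × 100/√356 = 10.60. Average estimates from the two models differed by at most about 0.13 µm, and neither showed bias beyond simulation error.

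**Step 7: a chance imbalance in one trial.** A difference between arms of 3 to 10 percentage points in Spectralis versus Stratus use would move the estimate by 0.03 × 50 × 0.5 = 0.75 µm up to 0.10 × 50 × 0.8 = 4.0 µm. This is how the loss of precision arises. It is not a further, systematic error.

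**The case against.** The strongest reply is that the plan already handles what matters. One instrument per patient removes a constant offset from the outcome. Randomisation is stratified within site, and scan rules written by site suggest that device largely follows site. A randomised ANCOVA remains valid when a prognostic factor is left out. On an SE near 10.6 µm, a 1.8% saving is about 0.19 µm, or 1.96 × 0.19 = 0.4 µm of confidence-interval half-width, which will hardly change how a secondary endpoint is read. All of this stands, and it sets the point's low priority.

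The offset is also inferred. The cut-offs are retreatment thresholds applied together with the investigator's opinion. Nothing in the documents calls them equivalent, reports a measured difference, or says that a gap at the threshold holds across the thickness range. That stands too: 25 to 50 µm is what the cut-offs imply, and it should not be called a known error.

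A reader might go further and infer that the treatment difference is biased, or that the 25 to 45 µm shift in Step 3 carries into it. The documents do not support either reading, given one device per patient and randomisation within site.

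Finally, some material is unseen. Reading-center procedures are not supplied, parts of both documents are redacted, and SAP section 1 places table specifications in a separate document. A conversion or a by-device table could exist there. SAP 5.2.2 itself is visible and specifies none.

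The reply does not show that the covariate is on one scale. One device per patient leaves the offset in the baseline value, and no site term in the model absorbs it.

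**Conclusion.** The point holds as a minor one. The thickness ANCOVA in SAP 5.2.2 and Protocol 7.3.2 adjusts for a baseline that, on the plan's own cut-offs, probably mixes three scales. The expected cost is residual variance higher by 0.3% to 7.7% and a standard error higher by about 0.1% to 4%, with no systematic bias in the treatment difference. The top of the range needs the steepest slope, the smallest residual SD, the larger baseline SD and an even Stratus/Spectralis split together. The simulation, with less extreme inputs, gives at most about 1.8% in SE.

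These figures rest on assumed slopes, SDs and device mix, and on a constant offset equal to the cut-off gaps. If devices differ by a scale factor instead, change scores would not be fully comparable either; the documents do not settle this. Whatever the variance figures, a pooled mean baseline thickness is hard to interpret if the devices read differently.

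**What to change.** Before database lock:

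1. In SAP 5.2.2, add OCT device (Stratus, Cirrus, Spectralis; fixed per patient) as a main effect in the thickness ANCOVA, so that baseline thickness adjusts within device.
2. Record this as a change from Protocol 7.3.2, which specifies the same model. Otherwise the two documents will disagree.
3. If the reading center already converts readings to a common scale, say so in SAP 5.2.2 instead; no device term is then needed for this purpose.
4. In SAP 4.2, summarise baseline thickness by device as well as overall.

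The cost is up to 2 degrees of freedom and one table split. No new assessments are needed, but the sponsor should confirm that device is held as an analysable field, which the visible text does not show. A main effect deals with a constant offset only, not a proportional one.

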6.1 Exposure to Study Treatment(s)

Exposure to study treatment will be summarized by the number and percentage of participants receiving 0, 1, 2, or 3 injections for the DEX PS DDS treated group, or 0, 1, 2, 3, or 4 treatments for the laser photocoagulation treated group. The mean number of study treatments and the numbers of total study days will be calculated for each treatment group.

6.2 Treatment-Emergent Adverse Events

A treatment-emergent adverse event (TEAE) is an adverse event that occurs after the initiation of the study treatment (ie, the onset date is the same as or after the study treatment date), or an adverse event with onset prior to the study treatment that worsened in severity or became serious after the initiation of the study treatment.

The incidence of TEAEs will be calculated by treatment groups and presented as the number and percent of participants experiencing the TEAE during the study period. Summaries for TEAE data will be organized into the following: all TEAEs regardless of causality; treatment-related TEAEs; ocular TEAEs; and treatment-related ocular TEAEs. The number and percent of participants with TEAEs will be presented as follows:

- By primary system organ class in alphabetical order, and preferred term
- By primary system organ class in alphabetical order and by the severity (maximum severity)

Within each system organ class name, TEAEs will be tabulated by preferred term and sorted in descending order of frequency in the DEX PS DDS treated group and then by the laser photocoagulation treated group. A participant with multiple occurrences of the same preferred term within the reporting period will be counted only once for that preferred term.

In addition, TEAEs leading to discontinuation will be tabulated similarly.

Analysis for adverse events of special interest will be done for cataract and elevated IOP. Summary for cataract will be based on participants with phakic lens at baseline. MedDRA terms for AE of cataract and elevated IOP are listed in Table 6-1. Additional terms may be added before database lock when applicable.

Table 6-1 AE of Special Interest Terms

System Organ Class	Preferred Terms	Group
Eye Disorders	Cataract	Cataract AEs
	Cataract cortical	Cataract AEs
	Cataract diabetic	Cataract AEs
	Cataract nuclear	Cataract AEs
	Cataract subcapsular	Cataract AEs
	Lenticular opacities	Cataract AEs
	Ocular hypertension	Elevated IOP AE
	Angle closure glaucoma	Elevated IOP AE
	Borderline glaucoma	Elevated IOP AE
	Diabetic glaucoma	Elevated IOP AE
	Glaucoma	Elevated IOP AE
	Glaucoma Traumatic	Elevated IOP AE
	Gaucomatous optic disc atrophy	Elevated IOP AE
	Open angle glaucoma	Elevated IOP AE
Pigmentary glaucoma	Elevated IOP AE	
Normal tension glaucoma	Elevated IOP AE	
Investigations	Intraocular pressure increased	Elevated IOP AE
	Intraocular pressure fluctuation	Elevated IOP AE

Cataract AEs are limited to eyes classified as phakic at baseline.

The AE start/end day referring to initial treatment date will be presented in listings. The calculation is the same as study day described in section 2.2.

For each TEAE of a subject, the most recent treatment is defined as the most recent treatment prior to TEAE start. Most recent treatment date/day and TEAE start/end day referring to the most recent treatment will be presented in listings.

- Most recent treatment day = most recent treatment date – initial treatment date + 1.
- TEAE start/end day referring to the most recent treatment = TEAE start/end date - most recent treatment date +1.

The following imputation rules only apply to cases in which the start date for AEs is incomplete (ie, partly missing). The imputation is done in order to determine TEAE. The data collected on CRF (ie, partly missing) will be presented in listings.

Missing Month and Day

- If the year of the incomplete start date is the same as the year of the first dose of study treatment, the month and day of the first dose of study treatment will be assigned to the missing fields.
- If the year of the incomplete start date is before the year of the first dose of study treatment, *December 31* will be assigned to the missing fields.
- If the year of the incomplete start date is after the year of the first dose of study treatment, *January 1* will be assigned to the missing fields.

700 µg DEX PS DDS

Missing Month Only

- If only the month is missing, the day will be treated as missing and both the month and the day will be replaced according to the above procedure.

Missing Day Only

- If the month and year of the incomplete start date are the same as the month and year of the first dose of study treatment, the day of the first dose of study treatment will be assigned to the missing day.
- If either the year of the incomplete start date is before the year of the date of the first dose of study treatment or if both years are the same but the month of the incomplete start date is before the month of the date of the first dose of study treatment, the last day of the month will be assigned to the missing day.
- If either the year of the incomplete start date is after the year of the date of the first dose of study treatment or if both years are the same but the month of the incomplete start date is after the month of the date of the first dose of study treatment, the first day of the month will be assigned to the missing day.

[figure not shown]
If the stop date is complete and the imputed start date as above is after the stop date, the start date will be imputed by the stop date.

[figure not shown]
If the start date is completely missing and the stop date is complete, the following algorithm will be used to impute the start date:

- If the stop date is after the date of the first dose of study treatment, the date of the first dose of study treatment will be assigned to the missing start date.
- If the stop date is before the date of the first dose of study treatment, the stop date will be assigned to the missing start date.

6.3 Serious Adverse Events

The number and percent of participants reporting TESAEs will be summarized by type of event (ocular or non-ocular) and relationship to treatment.

700 µg DEX PS DDS

8. Other Analyses

8.1 Subgroup Analyses

China subgroup is defined as all China participants. All analyses will be performed for China subgroup.

8.2 Interim Analyses

No interim analysis will be performed for this study.

[REDACTED]

10. References

11. Amendments

To be added when occurred.

ALLERGAN

Ozurdex China 206207-026 SAP

Date (DD/MMM/YYYY)/Time (PT)

Signed by:

Justification
